*** Provide the maximum number of individuals that**

1. May participate in any study interaction or intervention (Including screening, consenting, and study activities)
AND/OR
2. You obtain any data/specimens about (regardless of identifiability)

at VCU and at other sites under the VCU IRB's oversight. See the help text for additional guidance.
100

If this is a multi-Center Project, what is the maximum anticipated number of subjects across all sites?

*** Provide justification for the sample size by explaining how you arrived at the expected number of participants and why this number is adequate for answering the research questions:**

The study by Yannakoulia et al. (8) showed a 152 ± 190 (mean \pm SD) kcal lower food intake during the ad libitum meal for the smoking group compared to the sham group, 45 minutes after the 15-minute smoking/sham condition. Assuming a more conservative mean difference in food intake between the vaping and control condition in our study of 100 ± 200 (mean \pm SD) kcal (effect size of 0.50) following similar procedures (20 min vaping condition followed by a 45 min break before the food intake test), the sample size needed to detect a significant difference between the two conditions with a power of 80% and an α -level of 0.05 (two-sided) is 34.

Including ineligible individuals and expected dropout, we estimate up to 100 individuals may be consented over the course of the study. Please note that initial telephone/web screening is performed under separate protocols - HM20007677 and HM20002567.

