- 1. A statement explaining the study design**
- 2. A detailed description of all the procedures that will be followed to carry out the study, preferably in sequential order, and in sufficient detail that the study's methods could be replicated**
- 3. The schedule and frequency of when and how procedures will be conducted (e.g. in person, online, phone, paper, etc.)**
- 4. A description of all research measures/tests/interventions that will be used, including analyses/tests conducted on specimens/biological samples (if applicable)**

See the help text for additional guidance

Overview. This study involves 34 ECIG users who will complete 2, within-subject, laboratory conditions that differ by the product used: 1) JUUL e-cigarette with a 5% nicotine pod (tobacco flavor), 2) no ECIG use / participants sit in an empty room with an uncharged JUUL loaded with an empty pod for 20 minutes. The condition orders (i.e., 1 then 2, or 2 then 1) will be randomly ordered and assigned following enrollment. New recruits will replace participants who do not complete the study. Accrual ends when the required number of completers (N=34) is reached.

Products. For the session involving e-cigarette use, we will provide a pre-charged JUUL e-cigarette device and a new nicotine-containing pod containing (labeled as 5% nicotine; nicotine content will be verified independently for a random selection of products). The e-cigarette products will be sourced commercially (e.g., <https://www.juul.com/>). Please note we are unable to test each pod used during the study as accessing the liquid for testing requires tampering with the pod seal.

The anticipated amount of nicotine that will be absorbed with 20 puffs of this e-cigarette product is approximately 1.6 mg (Goniewicz et al., 2018, High exposure to nicotine among adolescents who use Juul and other vape pod systems ('pods'). Tobacco Control), which is equal to approximately 1.5 cigarettes (Digard et al. 2013. Determination of Nicotine Absorption from Multiple Tobacco Products and Nicotine Gum. Nicotine Tob Res).

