The session times were chosen to minimize the discomfort participants may experience due to extended abstinence from food/tobacco. Participants will also be asked to sign a form stating whether or not they have been abstinent from beverages (other than water), food, and tobacco/nicotine for ≥ 12 hours. In addition, participants will have their blood pressure checked and be asked about any side effects/adverse events experienced since the last visit. Responses to these items will determine whether participants can continue with the session/study.

Once deemed abstinent and safe to participate, participants will begin a 1-hour waiting period. During this time, participants cannot eat or use their cell phones, although water and/or books/magazines will be provided. We have recently instituted this 1-hour waiting period in other studies, because we find, after looking at plasma nicotine levels which are analyzed months after participants complete studies, that some participants do not comply with the 12-hour nicotine/tobacco abstinence requirement. Adding this 1-hour waiting period ensures that all participants are abstinent for at least one hour before the session begins.

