Pre-session side effects/adverse events. Before each session begins we ask participants whether they have experienced specific respiratory/gastrointestinal/other symptoms (identical to measures collected at baseline) as well as any other changes in their health since their last visit. Answers given at the beginning of each session will be compared to the participants' previous answers, and if any symptoms have increased or new information is provided that may raise participant risk/influence study data collection, [name] will be asked to review participant responses. In some cases, we may contact [name] to determine if a session can proceed. Premenopausal women also will be asked about their menstrual cycle.

Session physiological measures. To measure compliance with tobacco/nicotine abstinence at the beginning of sessions, a BreathCO monitor will be used (Vitalograph, Lenaxa, KS). For safety purposes, blood pressure will be checked at the beginning and end of each session. Energy (kcal) and macronutrient intake via will be measured via directly weighed food provision and waste (food intake is calculated by difference).

Session subjective measures. Repeatedly within each condition, we will ask participants to complete items that originate from the following questionnaires: Food Craving Questionnaire-State, Visual Analog Scales. See measures document for more detail.

Data analysis (**Statistical Analysis Plan**). Subjective and physiological data will be prepared as reported elsewhere (Barnes et al., 2017; Rusted et al., 1998; Cobb et al., 2010). In general, analysis will involve a within-subject ANOVA or mixed linear models approach. For all ANOVAs, adjustments for sphericity violations and post-hoc testing using Tukey's HSD or planned contrasts with Bonferroni corrections will be used (Keppel, 1991). Depending on the amount of missing data, multiple imputation techniques may be used (Allison, 2001).

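### Does replacing non-completers until there are 34 completers, with no stated analysis set, put the vaping comparison at risk?

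*Combined protocol and SAP*

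**What the plan says.** The sample-size justification under Study Population assumes a mean within-person difference "in our study of 100 ± 200" kcal (mean and SD), "with a power of 80"%, and concludes that the number needed at an alpha "level of 0.05 (two-sided) is 34". It anticipates losses: "Including ineligible individuals and expected dropout, we estimate up to 100 individuals may be consented over the course of the study". No dropout rate is given.

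The Overview under Study Procedures describes a two-condition within-subject design with the order randomised after enrolment, and sets the accrual rule: "New recruits will replace participants who do not complete the study. Accrual ends when the required number of completers (N=34) is reached".

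The Data analysis (Statistical Analysis Plan) paragraph says "In general, analysis will involve a within-subject ANOVA or mixed linear models approach", and on incomplete data, "Depending on the amount of missing data, multiple imputation techniques may be used".

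The Detailed Procedure has blood pressure checked and side effects since the last visit asked about at the start of each session, and adds: "Responses to these items will determine whether participants can continue with the session/study". The section on pre-session side effects and adverse events describes this as a review of changed or new symptoms, with a decision in some cases on whether that session goes ahead.

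No section names an analysis set or says what becomes of a replaced participant's first-session meal.

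**The concern.** An accrual rule says when to stop recruiting, not whose data count. Sessions are about a week apart and food is weighed at each, so a participant who leaves between them can contribute one valid meal. A within-subject ANOVA in its usual form drops that meal, a likelihood-based mixed model keeps it, and multiple imputation keeps it and fills in the missing session. Choosing the model therefore also chooses the participants, and nothing requires the choice to be made before the data are seen.

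Losses might also be related to treatment. Before session 2, participants report side effects since session 1, and session 1 was either 20 puffs at 5% nicotine or no vaping. If those who left also ate unusually much or little, the remaining pairs would misstate the effect even if the true effect were the same for everyone.

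**Working it through.** **1. The planned number.** Inputs from the sample-size justification: difference 100 kcal, SD 200, so d = 100/200 = 0.50; two-sided alpha 0.05; power 80%. A paired t-test (noncentral t) has power 0.795 at N = 33 and 0.808 at N = 34, so 34 reproduces. The standard error of the paired mean is 200/√34 = 34.3 kcal.

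**2. What one-session meals add in precision.** The within-person correlation ρ is not stated. The cited smoking study's SDs (245 and 310 in the background, 190 for the difference in the sample-size text) imply ρ = (245² + 310² − 190²)/(2·245·310) = 0.79; 0.50 is taken as a lower assumption. Assume dropout of 10%, 20% or 30%, every leaver having one meal, equal numbers in each order, and known variances. The standard error then goes from 34.30 to:

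| Dropout | ρ = 0.79 | ρ = 0.50 |
|---|---|---|
| 10% | 34.10 | 33.83 |
| 20% | 33.86 | 33.28 |
| 30% | 33.55 | 32.60 |

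The gain is at most 1.7 kcal (34.30 − 32.60). Power does not turn on the analysis set.

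**3. What completers-only bias requires.** Suppose selection in one sequence shifts its completers' session-1 intake by k within-condition SDs. Their session-2 intake shifts by ρk SDs, so their paired difference shifts by (1 − ρ)·SD·k. If that sequence supplies a fraction w of the completers, the bias in the mean is w(1 − ρ)·SD·k. The within-condition SD is 200/√(2(1 − ρ)): 200 kcal at ρ = 0.50 and 309 at ρ = 0.79.

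*Leaving depends on condition only.* Then k = 0 and the bias is zero. Simulations with 30% or 50% loss in vaping-first participants and 5% in control-first gave completers-only means of about 100 kcal (100 to 103 at the widest across runs) against a true 100.

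*Leaving depends on condition and intake (hypothetical).* In one sequence, 70% of the lowest third of eaters leave, and 5% of everyone else.
- Retained in that sequence: 0.30/3 + 0.95·2/3 = 0.733. Overall dropout: 1 − (0.733 + 0.95)/2 = 16%.
- The normal mean is −1.09 SD in the lowest third and +0.545 SD in the rest, so k = (0.100·(−1.09) + 0.633·0.545)/0.733 = 0.322.
- w = 0.733/(0.733 + 0.95) = 0.436.
- Bias at ρ = 0.50: 0.436·0.50·200·0.322 = 14.0 kcal. At ρ = 0.79: 0.436·0.21·309·0.322 = 9.1 kcal.

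Simulated completers-only means agree: 86 to 91 kcal or 109 to 115 kcal, depending on which sequence and which third leave; the mixed model gave 99 to 101. In the understated cases, paired-test power falls from about 81% to 69–74%. If the two sequences are weighted equally, as with a period term, w = 0.5 and the bias is 16.1 or 10.4 kcal, up to 16.1/34.3 = 0.47 standard errors. This is not a ceiling, because the dropout rate and pattern are assumed.

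With 35% and 3% in place of 70% and 5% (8% dropout), simulated means were 93 to 96 or 105 to 106 kcal.

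**4. Total error.** Root mean squared error in simulation, completers-only against mixed model: 35.0–37.4 against 34.7–35.1 kcal at 16% dropout; 34.5–34.8 against 34.7–34.8 at 8%. Under condition-only dropout the mixed model was equal or slightly worse (34.4–35.6 against 33.7–34.9).

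**The case for a change.** The strongest case for acting is that a sentence in the SAP costs nothing, the protocol itself expects dropout, and the side-effect review before session 2 could act differently by sequence. Fixing the set in advance would remove a choice that moves the estimate by 9 to 15 kcal in the 16% scenarios. It is also true that the required number of completers is an accrual target, and that no sentence excludes other participants' data.

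The silence stands as a fact. The consequence is weaker. The side-effect review gives at most a link to condition; nothing ties those answers to calories eaten, and without that second link the bias disappears. Large losses driven by the vaping session are not obvious either: participants are regular e-cigarette users, and anyone unwilling to take the 20 puffs is excluded.

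One qualification remains. Condition-only loss can leave the two orders unequal in size, and an unadjusted mean then absorbs any period effect: with a 20/14 split and an assumed 50 kcal period effect, 50·(20 − 14)/34 = 8.8 kcal. That concerns a period term, not the analysis set. A completers analysis with the term is free of it, and an all-randomised analysis without the term is not protected.

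The all-randomised set is also no complete remedy. If 8 leavers had a true effect of 200 kcal, the average over all 42 would be (34·100 + 8·200)/42 = 119, while the mixed model would move from 100 only to between 100 and 108.

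**Conclusion.** No change follows. This is a gap that analysts can fill sensibly from what is written. Paired sizing and recruitment to 34 completed pairs point to a completers analysis; if single-session meals are kept, the SAP already permits the model that does so. Replacing non-completers is not an error: it protects the planned power of 0.808.

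The two readings give nearly the same answer unless leaving depends jointly on first-session condition and intake. Under an assumed concentrated pattern with 16% dropout they differ by about 9 to 15 kcal, less than half a standard error for the unadjusted mean; at 8% dropout total error is practically the same. Dropout related to condition alone gives no meaningful difference, provided there is no period effect or it is in the model. These figures rest on assumed dropout rates and patterns, ρ between 0.50 and 0.79, a common true effect of 100 kcal and an SD of the difference of 200 kcal. Heavier joint selection would produce a larger bias, but the documents give no reason to expect it.

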After the one-hour waiting period, participants are asked to either vape (20 puffs) or will complete the control condition, which involves the participant sitting with an uncharged JUUL loaded with an empty pod for 20 minutes. The anticipated amount of nicotine that will be absorbed with 20 puffs of a 5% nicotine JUUL pod is approximately 1.6 mg, which is equal to approximately 1.5 cigarettes. They then have an additional rest period which is followed by an ad libitum buffet meal (that is administered in a different laboratory room). This rest period is to allow for feelings of satiety to occur prior to completion of the Food Craving Questionnaire, which measures appetitive drive to eat. We will use unobtrusive video surveillance of the participants during the buffet meal (Zoom) that will be monitored by research staff via their VCU computers (video data is transmitted via internet) during the ad libitum buffet meal. Live video will be monitored using privacy screens to ensure confidentiality during sessions and data will not be stored or linked to participant IDs or used for any analysis purpose other than determining if an individual takes food (other than eating it) from the laboratory room during the session. Immediately before and after the vaping/control condition, as well as immediately before and after the ad libitum meal, participants fill out subjective questionnaires. At the end of the session, participants will have their blood pressure checked again.

A detailed timeline of each session is described below.

Experimental session timeline (times approximate):

0 Hr 00 Participant arrives, Sign document/CO test/BP check/side effects-adverse events questionnaires followed by 1-hour waiting

0 Hr 05 Rest Period #1 begins
1 Hr 05 Subjective questionnaires
1 Hr 10 Vaping or control condition (uncharged JUUL w/ empty pod))
1 Hr 30 Subjective questionnaires
1 Hr 35 Rest Period #2 begins (additional questionnaires/behavioral tasks)
2 Hr 10 Subjective questionnaires
2 Hr 15 Ad libitum buffet meal
2 Hr 45 Subjective questionnaires
2 Hr 50 BP check, Pay participant and schedule next session if needed

Measures.

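### The side-effects/adverse-events form is given only on arrival, before exposure, so participants who vape in session 2 have none scheduled after using the study product (minor)

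*Combined protocol and SAP*

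**What the plan says.** Three places in the combined protocol and SAP fix the timing of the form.

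- The measures paragraph headed Pre-session side effects/adverse events: "Before each session begins we ask participants whether they have experienced specific respiratory/gastrointestinal/other symptoms". It adds: "Answers given at the beginning of each session will be compared to the participants' previous answers". The same items are also collected at the baseline screening visit.
- The Detailed Procedure, for arrival at each session: participants will "be asked about any side effects/adverse events experienced since the last visit". On the arrival checks as a group it says: "Responses to these items will determine whether participants can continue with the session/study".
- The experimental session timeline: "0 Hr 00 Participant arrives, Sign document/CO test/BP check/side effects-adverse events questionnaires followed by 1-hour waiting".

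The vaping or control period starts at 1 Hr 10. After it the timeline lists subjective questionnaires at 1 Hr 30, 2 Hr 10 and 2 Hr 45, and a second rest period: "1 Hr 35 Rest Period #2 begins (additional questionnaires/behavioral tasks". The closing entry is "2 Hr 50 BP check, Pay participant and schedule next session if needed". Under Session physiological measures the plan states: "For safety purposes, blood pressure will be checked at the beginning and end of each session".

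The Overview gives 34 completers, two conditions per person and a random order of conditions. The sessions are about a week apart.

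**The concern.** In both sessions the named symptom form comes before the exposure and asks about the period since the last visit. What happens after vaping can reach this form only at a later visit. Participants who vape first have such a visit if they return. Participants who vape second do not, because the plan describes nothing after session 2.

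The form's reach after vaping is therefore set by the randomised order. The mirror image holds for the control condition, where symptoms can reach the form only for those who have control first. The trial is within-subject, yet this form cannot give a within-subject comparison of symptoms by condition.

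The answers that do arrive are also hard to attribute. They come about a week after vaping, from people who were enrolled because they use e-cigarettes regularly and who are asked to abstain only for the 12 hours or more before a session. Comparison with each person's earlier answers helps, but cannot separate study vaping from own-product use in the same week.

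What is at stake is descriptive: how many participants are asked these questions after using the study product, and how soon. No efficacy result depends on it.

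**Working it through.** **The plan's own figure.** The only sample-size figure is 34. A paired t-test with a mean difference of 100 kcal and an SD of 200 kcal (effect size 100/200 = 0.50), two-sided alpha 0.05, has power 0.795 at n = 33 and 0.808 at n = 34. So 34 reproduces. It serves here only as the number of completers.

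**Timing within a session** (timeline; the plan calls its times approximate).

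- Form to start of exposure: 1 Hr 10 − 0 Hr 00 = 70 minutes, with the form first.
- End of exposure slot to closing step: 2 Hr 50 − 1 Hr 30 = 80 minutes. The form is not listed anywhere in this stretch.

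**Which administrations can follow study vaping, by order.**

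| Administration | Vape first, control second | Control first, vape second |
|---|---|---|
| Baseline symptom items | before vaping | before vaping |
| Session 1 arrival | before vaping | before vaping |
| Session 2 arrival | about a week after vaping | before vaping |
| After session 2 | none described | none described |

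The vape-first order has one scheduled form after vaping, reached only if the participant returns. The control-first order has none.

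**How many participants.** The plan says the order is random but gives neither the ratio nor any blocking.

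- Balanced orders (assumption): 34 × 0.5 = 17 completers vape in session 2.
- Simple randomisation with equal probability (assumption): X ~ Binomial(34, 0.5). P(X ≤ 10) = 0.0122, and by symmetry P(X ≥ 24) is the same, so P(11 ≤ X ≤ 23) = 1 − 2 × 0.0122 = 0.976.

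The number of completers with no form after vaping is thus about 17, with 11 to 23 as the likely range.

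**What a form at the closing step would add.** It would fall in all 34 vaping sessions and all 34 control sessions of the completers, about 80 minutes after the exposure slot ends, whatever the order.

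These counts describe coverage of the form. They are not event rates.

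**The case against.** The strongest reply is that the form does the job it was given. It is labelled as a pre-session measure, and its answers feed the decision on whether a participant continues. Such a check belongs before exposure. The stated aims are calories ingested and associated subjective effects, and no safety endpoint is named. All of this stands, and it is why the arrival form should not be moved.

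A second reply is that other post-exposure information exists. Blood pressure is checked at the end of each session for safety, and staff can speak with participants over the Zoom intercom. Visual analog scales and further questionnaires follow the exposure and may contain symptom items. Their content is deferred to a measures document that is not part of the text. The text is itself abstracted from review-board forms, and the application sent to the FDA is not shown either. Spontaneous reporting or later contact may be described in those sources.

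This limits what can be claimed. A reader might infer that symptoms after vaping are never recorded, or that the trial has an established gap in safety information. The documents support neither, because the instruments that could fill the gap are named but not shown. What remains is narrower: this form, on the schedule as stated, is never given after study vaping to those who vape in session 2. Blood pressure does not record respiratory or gastrointestinal symptoms, and an intercom is not a scheduled form.

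A third reply concerns the remedy. At the closing step participants have just eaten from a buffet after a long fast, so gastrointestinal answers would mix meal and vaping effects, and the trial expects intake to differ by condition. This also stands; the control session separates the two only in part.

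**Conclusion.** The point holds as a minor design improvement. The named side-effects/adverse-events form is scheduled only before exposure. About 17 of 34 completers (11 to 23 with 97.6% probability under simple randomisation) have no such form scheduled after using the study product, and the rest answer about a week later. The count assumes an equal chance of each order, which the plan does not state. The statement that nothing follows session 2 rests on the text available.

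A reader might also infer that the main result is at risk. It is not: the form plays no part in measuring food intake, and the calorie contrast, the sample size and the randomisation are untouched.

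**What to change.** Leave the arrival form as it is. Repeat the same symptom items at the 2 Hr 50 step of both sessions, after the meal, with the recall window reworded to run from the start of that session. Tabulate the answers descriptively by condition, with no formal test. Because the items come after the meal, they cannot influence intake in that session. Because they are asked in both sessions, their coverage no longer depends on order.

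The cost is a few minutes per session, a reworded recall window, a small amendment and one descriptive table. Two limits should be stated with the table: the repeat covers the session only, not the days after it, and gastrointestinal answers follow the buffet, so a difference between conditions cannot be read as an effect of vaping alone.
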